Statistical Plan: Demographic and clinical characteristics of each study group will be described. Descriptive statistics, including proportions means and standard deviations and medians and interguartile ranges will be used to summarize BCG-stimulated immune response and NTMinduced cytokine and NTM killing activity at each time point (0, 30 days and 90 days) for each study group. Log-transformations of markers will be performed if distributional assumptions indicate. The primary statistical procedures will utilize linear mixed models to evaluate the mean difference in each marker from time 0 to 30 days and from time 0 to 90 days. The model takes the following form: $E[Y_{ij}] = b_0 + b_1 time_j + b_2 group_i + b_3 group * time + a'z_i + \alpha_i$ where Y_{ij} is the marker of interest for subject i at time j, group denotes the CF/NCFB/control status, time is a numeric visit number, z_i can include a vector of potential confounders and α is a subject-specific random effect to account for within-person correlations of the outcome while assuming the outcomes follow a Gaussian distribution. The parameter b₃ is the parameter of interest here as it quantifies the effect of CF/NCFB status on changing markers from baseline. Importantly, this model specifically allows us to account for baseline differences between groups, if they do exist. Secondary analyses will leverage the full longitudinal data collection of each of the three time points utilizing the previously described methods.

Interim Analysis: An interim safety assessment will be conducted once 30 CF, 30 NCFB, and 30 healthy controls have been enrolled and have completed the intradermal BCG vaccination and the 30-day blood draw.

d. Early stopping rules.

If there are two or more of the same Grade 3 adverse events (severe or medically significant but not immediately life threatening; hospitalization or prolongation of hospitalization indicated; disabling; limiting self-care or ADLs), or a single Grade 4 adverse events (life threatening consequences; urgent intervention indicated), the study will be halted until the Data Safety Monitoring Board (DSMB) can meet to discuss the appropriate actions that should be taken.

8. Risks

a. Medical risks, listing all procedures, their major and minor risks and expected frequency.

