Following BCG vaccination, it is expected that nearly all individuals will exhibit a positive tuberculin skin test (also referred to as a purified protein derivative test or PPD) for a period of approximately five to seven years. Thus, latent TB testing via PPD method may be confounded by BCG vaccination. However, latent TB status can still be accurately determined by diagnostics blood tests (ex: QuantiFERON-TB Gold and ELISPOT TB).

Common adverse events from intradermal BCG vaccination include pain at injection site, a local skin reaction at the site of vaccination, which may ulcerate and scar, cause regional suppurative lymphadenitis, and osteitis, a rare complication (approx. complication rate

0.39/1,000,000). The most serious complication of BCG vaccination is disseminated BCG infection. The most frequent disseminated infection is BCG osteomyelitis (0.01 to 43 cases per 1,000,000 doses). Fatal disseminated BCG infection has occurred at a rate of 0.06-1.56 cases/1,000,000 doses. These primarily have occurred in immunocompromised hosts who are excluded from participating in this study.

There are rare case reports that vaccination against other viral infections, including SARS-Co-V2 and influenza, can cause transient erythema at the site of previous BCG vaccination, with no longterm clinical consequences.

Rarely, BCG vaccination can lead to transient vaccine-induced lymphadenopathy, which may present diagnostic dilemma for women undergoing screening mammography for breast cancer.

Common adverse events from routine blood draws include mild pain at blood draw site, minor bleeding and/or bruising.

b. Steps taken to minimize the risks.

Experienced nursing and research staff from the JH CIR will perform the intradermal vaccinations and study blood draws.

To minimize concerns, we are excluding individuals with immunosuppression, children, elderly, and pregnant/breastfeeding participants.

To minimize confounding results on mammography, female participants will be advised to delay screening mammography performed for a minimum of 3 months following BCG vaccination.

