We will adhere to guidance on DSMB activities (see attachment). The data and safety monitoring plan will include reporting any adverse events to the IRB and the DSMB in the quarterly progress reports. In addition, we have a detailed plan on how to deal with serious adverse events that may arise, which will include reporting to the chair of the DSMB and IRB within 24-hours of notification. The study will be conducted according to the FDA's Good Clinical Practice Guidelines.

A DSMB has been created to function as an independent group of experts who will advise the study investigators. The members of the DSMB will serve in an individual capacity and provide their expertise and recommendations. The members are not co-investigators of the study and have no undisclosed conflict of interest.

Safety Monitoring Plan:

Following BCG administration, participants will be instructed to contact the investigative team if she or he experiences symptoms such as fever of 101.5°F or greater, or acute localized inflammation persisting longer than 2-3 days, which would be suggestive of active infections. If an illness of this degree has occurred, an evaluation for a serious infectious complication will be performed which includes consultation with an infectious disease physician. In individuals who develop persistent fever or experience an acute febrile illness consistent with BCG infection,

two or more antimycobacterial agents will be administered while diagnostic evaluation, including mycobacterial blood cultures are conducted.

The DSMB will also be charged with reviewing any complaints from patients, family members, and clinicians about any aspect of the study including recruitment procedures and study implementation. All potential participants will be provided with contact information to register complaints, if they experience adverse events, coercion or other problems. Participant complaints will be reported to the IRB pursuant to Hopkins policies. The DSMB will modify or stop the study if any such complaints represent a legitimate concern about the study procedures or methods.

The DSMB has the authority to halt the study if it perceives that harm is occurring due to the intervention.

c. Plan for reporting unanticipated problems or study deviations:

All unanticipated problems or study deviations will be reported per standard Johns Hopkins IRB procedures.

d. Legal risks such as the risks that would be associated with breach of confidentiality.

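### The automatic halt rule in section 7d does not pause vaccination after a first disseminated BCG infection graded 3, the complication the plan calls most serious

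*Combined protocol and SAP*

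**What the plan says.** Section 7d (Early stopping rules) has two triggers. The first reads "If there are two or more of the same Grade 3 adverse events (severe or medically significant but not immediately life threatening; hospitalization or prolongation", and its definition goes on to disability and loss of self-care. The second is "a single Grade 4 adverse events (life threatening consequences; urgent intervention indicated), the study will be halted until the Data Safety Monitoring Board". No event is singled out by name.

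Section 8a (Medical risks) states: "The most serious complication of BCG vaccination is disseminated BCG infection". It then gives rates: "The most frequent disseminated infection is BCG osteomyelitis (0.01 to 43 cases per 1,000,000 doses") and "Fatal disseminated BCG infection has occurred at a rate of 0.06-1.56 cases/1,000,000 doses". It adds: "These primarily have occurred in immunocompromised hosts who are excluded from participating in this study". Among the common adverse events it separately lists that vaccination may "cause regional suppurative lymphadenitis, and osteitis, a rare complication", the last at about 0.39 per million.

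The other safeguards are these:
- **Section 8b, reporting.** There is a plan for serious adverse events, "which will include reporting to the chair of the DSMB and IRB within 24-hours of notification".
- **Section 8b, DSMB.** The DSMB may halt the study if it perceives harm from the intervention.
- **Section 8b, clinical management.** A persistent fever or a febrile illness suggesting BCG infection leads to antimycobacterial treatment while the diagnosis is worked up.
- **Section 8c.** Unanticipated problems go to the IRB.
- **Section 7c.** An interim safety assessment follows once 30 participants per arm have been vaccinated and have had the 30-day blood draw. No pause in vaccination is attached to it.

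Every participant receives one dose and no booster (sections 4f and 4h).

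**The concern.** The rule treats the complication that the plan itself ranks worst like any other Grade 3 event: it waits for a repeat. The vaccine is live and given once, so a pause can protect only people who have not yet been vaccinated. Its value lies in its timing. If a first case pointed to a fault in preparing the dose or in screening, the next participant could be exposed to the same fault before a second case appeared.

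What is at stake is participant safety in an unlikely event. The trial's estimates and tests do not depend on it.

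**Working it through.** **Step 1: apply the rule to one case.** Take a first disseminated BCG infection, for example osteomyelitis, that needs admission but is not life-threatening. By 7d's own definitions it is Grade 3.

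| Trigger in 7d | Count needed | Count after the first case | Halt? |
|---|---|---|---|
| Same Grade 3 event | 2 | 1 | No |
| Grade 4 event | 1 | 0 | No |

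There is no automatic halt. The plan states no operating characteristics for this rule, so there is no figure of its own to reproduce.

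**Step 2: compare with the other safeguards.** The 24-hour report informs the DSMB chair and IRB. The DSMB's authority is discretionary. The interim assessment is tied to enrolment, not to an event. In the supplied text, none of these stops the next dose by itself.

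**Step 3: scale at the plan's own rates.** Inputs: n = 60 + 60 + 60 = 180 doses (sections 4a and 4f), and p = 0.01 to 43 per million for osteomyelitis (section 8a). Independent, equal risks are assumed.

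- Expected cases: 180 × 0.00000001 = 0.0000018, up to 180 × 0.000043 = 0.00774.
- At p = 0.000043, P(at least 1) = 1 − (1 − p)^180 = 0.00771, or 0.77%.
- P(exactly 1) = 180 × p × (1 − p)^179 = 0.00768.
- P(2 or more) = 0.00771 − 0.00768 ≈ 0.00003, or 0.003%.
- P(2 or more, given at least 1) = 0.00003 / 0.00771 ≈ 0.4%.

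At this rate, a rule that needs a second like case would almost never fire after a first.

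**Step 4: is one case a signal?** For 1 case in 180 doses, the exact (Clopper-Pearson) lower 95% limit is 1 − 0.975^(1/180) = 141 per million, and the upper limit is 30,563 per million. If the case came within the first 90 doses, the lower limit is 1 − 0.975^(1/90) = 281 per million. Both lower limits exceed the plan's maximum of 43 per million for osteomyelitis.

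**Step 5: if the true rate in this trial were much higher.** The rates below are assumptions for range and are not in the documents. All cases are taken as Grade 3.

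| Assumed rate | P(at least 1 in 180) | P(2 or more) | P(exactly 1) |
|---|---|---|---|
| 0.1% | 16.5% | 1.4% | 15.0% |
| 0.5% | 59.4% | 22.7% | 36.7% |
| 1% | 83.6% | 53.8% | 29.8% |

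The last column is the chance that a case occurs but the Grade 3 trigger never fires for it.

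**Step 6: fatal infection.** At the plan's upper rate, 180 × 0.00000156 = 0.00028 expected cases, or 0.028%. The documents give no all-cause death rate.

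**The case against.** The strongest reply is that the plan chose a grade-based rule backed by expert judgement, and that the judgement would work. A case needing admission would presumably count as a serious adverse event (the protocol does not define the term) and so reach the DSMB chair within a day. By Step 4, a single case would give the DSMB strong reason to act. Some cases would be graded 4, since that grade covers a need for urgent intervention, and would already halt. The DSMB attachment and the detailed serious-event plan cited in section 8b were not supplied and may contain a trigger. All of this stands, and it is why the point is narrow. What remains is that, in the supplied text, stopping the next dose depends on a grading call and a discretionary decision.

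It can also be said that the risk is negligible because immunocompromised people are excluded. That stands only in part. The sentence on immunocompromised hosts directly follows the one on fatal cases, so applying it to osteomyelitis is one reading. The only HIV test listed is for healthy volunteers (section 5 and Appendix A); CF and NCFB participants are screened by chart review and phone (section 4a).

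A reader might infer three stronger points. The documents do not support them:
- **That nothing would stop the trial after a first case.** The DSMB would be informed and could halt.
- **That 0.77% caps the risk.** Section 8a calls osteomyelitis only the most frequent disseminated form and gives no total. In the other direction, the figure includes Grade 4 cases that already halt and cases arising after the last dose.
- **That a death would not halt the study.** Section 7d does not name death, but a fatal event would ordinarily pass through the Grade 4 definition. This is a drafting gap only.

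**Conclusion.** The concern holds in a limited form. As written, 7d does not automatically pause vaccination after a first disseminated BCG infection graded 3, and the safeguards in 7c, 8b and 8c report or permit action without requiring a pause. The event is improbable at the plan's quoted rates. The 0.77% and 0.003% figures show scale for osteomyelitis under equal, independent risk in 180 doses; they do not bound the risk of all disseminated infection. The conclusion assumes that the unsupplied DSMB attachment and serious-event plan contain no such trigger. If they do, 7d need only refer to it. This is a cheap, low-priority safety improvement.

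**What to change.** Add one sentence to 7d: any death, or a single confirmed disseminated BCG infection of any grade (including BCG osteomyelitis), pauses further vaccination until the DSMB has reviewed it. Leave the existing Grade 3 and Grade 4 triggers unchanged.

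Do not add osteitis as a separate trigger; section 8a lists it apart from disseminated infection. Do not extend the trigger to suspected cases. If suspicion were defined as starting the antimycobacterial treatment in section 8b, and 0.05%, 0.1%, 0.5% or 1% of participants started it (assumed rates), the chance of at least one pause would be 1 − (1 − p)^180 = 8.6%, 16.5%, 59.4% or 83.6%. Two of the three arms are prone to recurrent respiratory infection, so false triggers are plausible. The price of requiring confirmation is a later pause, with DSMB discretion covering the interval.

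The cost is a short protocol amendment and, if needed, a matching edit to the DSMB document. The downside is a rare, short pause until the DSMB meets: about 0.77% over 180 doses at the plan's upper osteomyelitis rate, with other disseminated forms not quantified in the documents.

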Appendix A: Schedule of sample collection

Study visit	Sample collection		
Screening visit (healthy volunteers	HIV ELISA, rapid antibody test and/or confirmatory test, if		
only)	necessary		
Visit 1	Urine pregnancy test		
	Blood draw (pre-BCG vaccination). Approximately 75cc		
	(total) of blood collected in: SST, lithium-heparin tubes,		
	PAXgene RNA, EDTA		
Visit 2 (Day 30 +/- 5)	Approximately 75cc (total) of blood: collected in: SST,		
	lithium-heparin tubes, PAXgene RNA, EDTA		
Visit 3 (Day 90 +/- 14)	Approximately 75cc (total) of blood: collected in: SST,		
	lithium-heparin tubes, PAXgene RNA, EDTA		

Appendix B: Schedule of study surveys/standardized instruments

Study visit	Healthy volunteers	CF	NCFB	
Visit 1 (Day 1)	Healthy Volunteer	CF Medical History	NCFB Medical History	
	Medical History Form	Form,	Form,	
		CFQR	QOL-B,	
			MRC Dyspnea Scale	
Phone call (Day 2)	Phone safety monitoring form (all arms)			
Phone call (Day 7 +/- 2)	Phone safety monitoring form (all arms)			
Visit 2 (Day 30 +/- 5)	Interval Medical History Form (all arms)			
Visit 3 (Day 90 +/- 14)	Interval Medical	Interval Medical	Interval Medical	
	History Form	History Form,	History Form,	
		CFQR	QOL-B,	
			MRC Dyspnea Scale	
Visit 4 (Day 180 +/- 45)	Interval Medical	Interval Medical	Interval Medical	
	History Form	History Form	History Form	

References:

- 1. Moorlag SJCFM, Arts RJW, van Crevel R, Netea MG. Non-specific effects of BCG vaccine on viral infections. *Clin Microbiol Infect Off Publ Eur Soc Clin Microbiol Infect Dis*. 2019;25(12):1473-1478. doi:10.1016/j.cmi.2019.04.020
- Arts RJW, Moorlag SJCFM, Novakovic B, et al. BCG Vaccination Protects against Experimental Viral Infection in Humans through the Induction of Cytokines Associated with Trained Immunity. *Cell Host Microbe*. 2018;23(1):89-100.e5. doi:10.1016/j.chom.2017.12.010
- 3. Crispen R. History of BCG and its substrains. Prog Clin Biol Res. 1989;310:35-50.
- 9. Kaushal D. The Comeback Kid: BCG. J Infect Dis. 2020;221(7):1031-1032. doi:10.1093/infdis/jiz117
